5.0 Study Procedures

5.1 Study Design

Specific Aim 1 – Respiratory-Swallow Training (RST) In-Clinic.

Patient Sample. A total of 51 participants will be enrolled with the goal of 40 recruited if they meet inclusion criteria. Forty participants will be randomly assigned (1:1) to either RST (intervention arm) or no active treatment (control arm), which is considered standard of care in this patient population. Participants assigned to the control arm will cross-over after 4 weeks of no active treatment to undergo RST. All patients will participate in a pre-RST MBSS. The purpose of this pre-RST MBSS is to identify their baseline pre-RST respiratory-swallow phase patterning by specifying the respiratory phase and volume at time of swallowing initiation, assess swallowing physiology (MBSImP) and assess clinical swallowing status (FOIS). Participants will be included in the study if they are able to swallow at least one liquid consistency without visible tracheal residue (PAS ≤ 6) and without the use of a compensatory strategy or swallow maneuver. Participants will be excluded if they have known allergy or dietary restriction for contrast materials or liquids used during the MBSS or training, currently drinking greater than two drinks per day, severe COPD, are unable to swallow one liquid consistency without the use of a compensatory strategy or swallow maneuver without aspiration, or history of aspiration pneumonia within the past 12 months.

Clinician Examiners, Raters and Trainers. Expert speech-language pathologists (SLPs) will participate in this study to provide RST training, conduct the MBSSs, and perform blinded MBSImP and PAS scoring (i.e., without benefit of patient identifiers, randomization, clinical information, and performance during RST). The SLPs will not crossover study roles.

Spirometry. All Veteran and non-Veteran participants will undergo PFTs using spirometry performed by American Thoracic Society standards to stage COPD.⁸⁸ Participants will be characterized into Global Initiative for Obstructive Lung Disease (GOLD) spirometric groups on the basis of % predicted FEV1.⁹⁰ Any patient with severe stage COPD will be excluded from the study to protect against risk since experience in our clinic and previous study showed these patients could not consistently perform the proposed training tasks.

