Data Management, Analysis, and Reporting System Overview. Study related data are stored on VA approved computers and the VA research shared drive (S:), including de-identified study-related data (videofluoroscopic images, respiratory traces). Identifiable data (VASA), including demographic data, questionnaire responses, and treatment results are stored on the VA REDCap behind the VA firewall. De-identified videofluoroscopic images and respiratory tracings will be transported via VA issued encrypted external hard drives for analysis by specially trained analytic experts to the PI's lab at Northwestern University, and then stored on and analyzed from a password protected, dedicated server. This server is managed by Northwestern Information Technology and accessible to only approved study personnel. We will update the data transfer and storage operations as we are provided additional guidance and requirements from the ORO, Office of Research Oversight.

Power and Sample Size Justification. A total of 40 subjects will be randomized 1:1 using stratified block randomization to either Respiratory-Swallow Training (RST, intervention arm) or no control arm, where the participants serve as their own control and then cross over into the intervention group. Strata will be defined by treatment type. Data obtained will be used to evaluate clinical efficacy and durability. The primary outcome measure will be MBSImp physiologic function metrics of the oropharyngeal swallow. Our previous preliminary trial that tested the safety and efficacy of the behavioral swallowing intervention in a small sample of Veteran and non-Veteran patient with head and neck cancer showed a positive change in the physiologic outcomes. Assuming a similar treatment effect in the current trial, 20 patients in each arm provides 95% power to detect a change in MBSImp physiologic function in at least one of three MBSImp components (laryngeal vestibular closure, tongue base retraction, and pharyngeal residue) based on a Cochran-Mantel-Haenszel test with two-sided $\alpha = 0.025$. Although dropouts have been rare in our prior studies, we nonetheless inflated our sample size by 10% to adjust for unanticipated attrition, and plan to recruit 20 participants per arm for a total sample size of 40 subjects to guarantee at least 80% power. Thus, our final sample size will be a total of 40 participants.

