Analysis Populations. Participants in the intervention arm who withdraw consent prior to completing their first training session will be replaced. Those who have completed at least one RST session will contribute to the intent-to-treat (ITT) population. Participants in the control arm who withdraw consent prior to visit 1 will be replaced. All others in the control arm will contribute to the ITT population. The per-protocol population will be composed of participants who complete both visit 0 and visit 1 evaluations (both arms), and who complete all required training sessions (intervention arm). Efficacy will be evaluated based on the ITT population. Participants in the ITT population who withdraw prior to endpoint evaluation at 6-weeks will be treated as failures (no improvement) in the ITT analysis. The safety population is defined as all participants

who partake in any component of the proposed study and will be based on the intervention actually received.

Specific Aim 2 Design and Methods – Intervention Impact of RST on Swallowing

Physiology. We will elaborate the treatment impact of RST by detailing the physiological, airway protective and morphometric changes that occur from the intervention. We will use MBSImP, PAS (described for Aim 1), and CASM.

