Children will not be eligible for enrollment in this project. Children do not commonly present with HNC. Further, respiratory-swallow phase patterns and training have not been systematically studied in dysphagic children. This supports their exclusion from this project that is based on preliminary data acquired in adults.

5.2 *Recruitment Methods*

A total of 51 Veteran and non-Veteran volunteers will be enrolled with the goal of 40 meeting inclusion criteria. Potential participant volunteers will be identified by the following methods of participant recruitment, all approved by the VA Institutional Review Board (IRB): 1) follow-up medical visits, particularly the otolaryngology-head and neck clinics; 2) announcement of the study in the VA patient bulletins and monitors (Appendix); 3) community-based outpatient clinics (CBOCs); and 4) review of patient medical charts (CPRS) at Hines VA to find patients that match the diagnosis of oropharyngeal cancer and dysphagia diagnoses (letters will be mailed to these potential patients with information in regards to the study. Also included will be a brief survey, along with a postage paid return envelope, which allows the patients to indicate if interested in participating or not); 5) posting of recruitment flyers at Jesse Brown VA, Loyola University Medical Center, Northwestern Memorial Hospital, University of Chicago Medical Center, and Northwestern Medicine Healthcare Partners.

Participants will be compensated for their participation in the study to assist support of their time and travel. Participants will receive \$40 for each MBSS and \$30 for each RST session. For participants randomized to immediately undergo the intervention, they have the potential maximum of earning \$440. The participants randomized to the control group will undergo one additional MBSS procedure immediately prior to their cross-over to the intervention arm, for a potential maximum of \$480. Participant payment will be made according to the current local fiscal office guidance and processes. Planned payments will be approved by appropriate study personnel for disbursement according to this schedule:

- Payment 1: after first study visit to determine eligibility for intervention (which includes first MBSS)
- Payment 2: after week 1 of intervention
- Payment 3: after week 2 of intervention
- Payment 4: after week 3 of intervention
- Payment 5: after week 4 (final) of intervention
- Payment 6: after post-intervention study procedures

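### The sample size statement does not match the analysis plan: 40 against 88 randomised, power for a test that Section 5.6 does not run, and a 95% with no inputs

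*Combined protocol and SAP*

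**What the plan says.** **Section 5.1, Power and Sample Size Justification.** Forty subjects are randomised 1:1. The text says that "20 patients in each arm provides 95% power to detect a change in MBSImp physiologic function in at least one of three MBSImp components". The components are laryngeal vestibular closure, tongue base retraction and pharyngeal residue. The test is Cochran-Mantel-Haenszel (CMH) at two-sided 0.025. The only effect assumption is an effect similar to the preliminary trial. On losses it adds: "we nonetheless inflated our sample size by 10% to adjust for unanticipated attrition, and plan to recruit 20 participants per arm", and then "for a total sample size of 40 subjects to guarantee at least 80% power". It describes the comparator as "no control arm, where the participants serve as their own control and then cross over into the intervention group".

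**Section 5.1, Analysis Populations.** Intervention-arm participants who withdraw consent before completing their first session are replaced. For controls: "Participants in the control arm who withdraw consent prior to visit 1 will be replaced". Others in the ITT population who withdraw before the endpoint "will be treated as failures (no improvement) in the ITT analysis".

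**Section 5.2.** "A total of 51 Veteran and non-Veteran volunteers will be enrolled with the goal of 40 meeting inclusion criteria".

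**Section 5.6.** The trial design paragraph recruits and randomises 88 participants in five strata. The Aim 1 primary analysis compares the arms on change in MBSImP metrics by ANACOVA, or by GEE with identity link if normality fails. It does not name the components, give a CMH test or state an alpha.

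**The concern.** A sample size statement should tie one number of patients to one test of one endpoint at one alpha. Here the two sections disagree on the number, the test and the endpoint. The power figure cannot be traced to inputs, and the attrition sentence returns the number it started from.

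A null result could then not be set against a known detectable effect. If one component of three were positive, a reader could not tell which error rate applied, because the relation of 0.025 to the three components is not stated.

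**Working it through.** **1. Number randomised**

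| Place | Number |
|---|---|
| Abstract | 51 recruited to reach 40 enrolled |
| 5.1, Patient Sample | 40 randomised 1:1 |
| 5.1, Power and Sample Size | 40 randomised, called final |
| 5.1, planned enrolment table | 40 |
| 5.2 | 51 to reach 40 eligible |
| 5.6, Trial design | 88 randomised 1:1 (44 per arm) |

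The 51 is a recruitment or consent figure and fits with 40. The 88 does not.

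**2. Powered test against planned test**

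| | 5.1 | 5.6, Aim 1 primary |
|---|---|---|
| Test | CMH | ANACOVA or identity-link GEE |
| Variable | at least one of three named components | change in unnamed MBSImP metrics (17 components, two scoring methods) |
| Alpha | 0.025 two-sided | none stated |

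**3. Attrition**

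- Adding 10% to 20 gives 20 × 1.1 = 22, not 20.
- A base of 18 fits: 18/0.9 = 20. The text does not state it, so it is unclear whether the 95% belongs to 18 or to 20.
- If 95% holds at 20 per arm for a single component, 18 per arm gives 92.3% at alpha 0.025 and 91.9% at 0.0083 (noncentral t, as in step 6). The 80% floor is compatible with this but is not derived from it.
- The ITT rule does not cut both arms to 18. Control consent withdrawals are replaced up to visit 1, the control arm's 4-week endpoint, while later intervention-arm withdrawals stay in as no improvement. With 2 of 20 intervention patients set to zero change, 95% falls to 89.0% to 90.1% (simulation, 200,000 trials, alpha 0.0083 and 0.025).

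**4. The 95%**

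It cannot be reproduced, because no inputs are given. As an illustration, use the Table 3 impairment rates before and after training: laryngeal vestibular closure 78.2% and 55.5%, tongue base retraction 96.0% and 88.6%, pharyngeal residue 96.1% and 88.4%. Assumptions: controls stay at the pre rate, m = 10 swallows per patient, independent components.

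- Effective size per arm: n_eff = n·m / [1 + (m − 1)·ICC].
- Power per component: Φ{[|p1 − p2|·√n_eff − z·√(2p̄(1 − p̄))] / √[p1(1 − p1) + p2(1 − p2)]}, where p̄ is the mean of p1 and p2.
- At least one of three: 1 − Π(1 − power).

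For n = 20 and ICC 0.1 at alpha 0.025 each, n_eff = 200/1.9 = 105.3. The component powers are 90.2%, 40.9% and 43.9%, so 1 − 0.098 × 0.591 × 0.561 = 96.8%.

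| ICC (assumed) | 20 per arm, 0.025 each | 18 per arm, 0.025 each | 20 per arm, 0.0083 each |
|---|---|---|---|
| 0.1 | 96.8% | 94.9% | 90.2% |
| 0.2 | 87.1% | 83.2% | 72.3% |
| 0.3 | 76.0% | 71.3% | 57.0% |
| 0.5 | 58.2% | 53.7% | 37.8% |

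**5. Alpha**

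If 0.025 applies to each component and any one counts as success, the family-wise error is 1 − 0.975³ = 7.3% under independence and at most 3 × 0.025 = 7.5%. If 0.025 is overall, it is 2.5%.

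**6. Detectable difference for the test in 5.6**

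ANACOVA with five strata has df = 2n − 2 − 4 and noncentrality d·√(n/2), with d in SDs of strata-adjusted change. For 95% on any one of three equal independent components, each needs 1 − 0.05^(1/3) = 63.2%. With full correlation, each needs 95%.

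| Alpha per component | Independent, 20 / 18 per arm | Fully correlated, 20 / 18 per arm |
|---|---|---|
| 0.025 | 0.85 / 0.90 SD | 1.28 / 1.35 SD |
| 0.0167 (0.05/3) | 0.90 / 0.96 SD | 1.33 / 1.42 SD |
| 0.0083 (0.025/3) | 0.99 / 1.05 SD | 1.43 / 1.52 SD |

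The documents give no mean or SD of a component score, so these differences cannot be compared with the pilot effect.

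**The case against.** **What stands.**

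- A base of 18 removes the attrition arithmetic problem, and a floor of 80% does not contradict about 92%. What is left there is an unclear sentence.
- Twenty in each arm, randomised 1:1, reads as a between-arm calculation, so the own-control phrase is a wording fault.
- The similar-effect assumption refers to a pilot that may hold the missing inputs.
- No section says that success on any one component is enough, so the 7.3% is conditional.

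**What does not rescue the statement.** Section 5.6 has a Rao-Scott test with Mantel-Haenszel-type adjustment, but it serves the respiratory-swallow phase patterns and is cited for the Aim 2 impairment rates. A CMH test can also handle ordinal scores, but it would still not be the Aim 1 primary test.

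**Stronger readings that the documents do not support.**

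- A reader might take Table 3 as one yes/no value per patient and infer that true power is far below 95%. Table 3 hardly fits that reading. Tongue base retraction falls by 7.4 points with p<0.0001. With one paired value per patient, an exact McNemar test needs at least 15 changes, all in one direction (2 × 0.5^14 = 0.00012; 2 × 0.5^15 = 0.00006). That means about 15/0.074 = 203 patients, while Section 5.1 calls the pilot sample small.
- A reader might infer that 88 is left over from an older calculation, since 88/1.1 = 80. The documents do not say so.
- A reader might infer that only early consent withdrawals are replaced. That is true of the intervention arm only.

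**Conclusion.** The point holds and should be fixed. Three parts rest on the text alone: 88 conflicts with 40; the power statement is for a different test and a differently defined endpoint from the Aim 1 primary analysis; and 20 per arm carries both the 95% and the inflation unless a base of 18 is supplied.

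The fourth part is that the 95% is unsupported. The range of 58.2% to 96.8% rests on assumed swallow counts, ICCs, independent components and an unchanged control arm. It shows that the figure depends on inputs not stated. It does not show that the trial is underpowered.

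The fifth part is conditional: family-wise error is 2.5% if 0.025 is overall, and 7.3% to at most 7.5% if it is per component and any one suffices.

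**What to change.** No patients are added.

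**In Section 5.6**

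- Change 88 to 40.
- Name laryngeal vestibular closure, tongue base retraction and pharyngeal residue as the primary family, and state how each is scored per patient (binary or ordinal; swallow-by-swallow or overall impression).
- Use the same between-arm primary test as in Section 5.1.
- State whether 0.025 is overall or per component, and apply Holm: at 0.025 if overall, at 0.05 if per component.

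**In Section 5.1**

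- Replace the 95% and the 80% guarantee with power, or a detectable difference, for that test at 20 and 18 per arm, showing rates or SD, unit, correlation and alpha. Keep 95% only if those inputs reproduce it. Without an SD, the ANACOVA table above can be used.
- State 18 as the base size, or delete the 10% claim.
- Describe losses as Analysis Populations has them: intervention-arm consent withdrawals before the first completed session and control consent withdrawals before visit 1 are replaced; other ITT withdrawals before the endpoint count as no improvement. Give the value this takes in the analysis, for example zero change.
- Reword the own-control phrase to match the randomised comparison.

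**Cost.** Wording only. The stated power may become less favourable, and the smallest p-value may face 0.0167 (Holm at 0.05) or 0.0083 (Holm at 0.025) in place of 0.025.

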5.6 Data Analysis

Statistical Considerations. Specific Aim 1: Trial design. The primary objective of Specific Aim 1 is to demonstrate the clinical efficacy and durability of RST in participants with dysphagia with a history of OP HNC. A total of 88 participants will be [recruited and randomly assigned 1:1 to either RST (intervention arm) or control arm, given the crossover design of the study. We will use a stratified permuted block randomization scheme with random block sizes of 2 or 4 to balance important prognostic variables across the two trial arms. There will be 5 strata defined by treatment modality (radiation therapy alone, surgery alone, chemo-radiation therapy, surgery + post-operative radiation therapy, surgery + post-operative radiation therapy + adjuvant chemotherapy). The study statistician will maintain randomization lists and be responsible for randomizing consented participants. The study schema is depicted in Figure 8. The control arm will cross over to RST after visit 1 following data collection for evaluation of clinical efficacy.

Endpoint Definitions and Analysis Plans. The primary efficacy endpoint for Aim 1 is oropharyngeal swallowing physiologic metrics (MBSImp) and evaluated at: visit 0, defined as pre-RST for intervention subjects, and baseline for control subjects; and visit 1, defined as post-RST for intervention subjects or 4 weeks post-baseline evaluation for control subjects. We will compare changes in MBSImp physiologic function metrics in patients randomized to intervention versus control. Change in MBSImp physiologic function metrics will be compared using one-way analysis of covariance (ANACOVA), with trial arm as the main effect and adjustment for stratification variable of treatment type. If approximate normality is not satisfied, we will use generalized estimating equations (GEEs) with an identity link function and robust standard error estimator. Furthermore, the regression framework of GEEs will accommodate adjustment for stratification factor. Durability of response will be evaluated using ANACOVA or GEEs as described by comparing post-RST MBSImp physiologic function metrics to those obtained at 1-, 3-, and 6-month follow-up visits. We will further evaluate the modifying and confounding effects of sex, age, smoking status, COPD status, and pulmonary function.

[figure not shown]

Figure 7 Study schema for current proposal.

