Further, response durability will be evaluated using FOIS measures obtained at 1-, 3- and 6-months post-RST. Because control subjects cross over to RST at visit 1, FOIS measures collected at visit 1 for control subjects additionally will serve as their pre-RST FOIS measures (Figure 7). Clinical efficacy will be evaluated by comparing change in FOIS (Δ FOIS = FOIS_{visit1} – FOIS_{visit0}) in patients randomized to intervention versus control. Δ FOIS comparisons will be conducted using one-way analysis of covariance (ANACOVA), with trial arm as the main effect and adjustment for stratification variables. If approximate normality is not satisfied, we will use generalized estimating equations (GEEs) with an identity link function and robust standard error estimator, which accommodates valid inference in the presence of misspecification.^{103,104} Furthermore, the regression framework of GEEs will accommodate adjustment for stratification factors. Durability of response will be evaluated using ANACOVA or GEEs as described by comparing post-RST FOIS measurements to those obtained at the 1-, 3- and 6-months follow-up visits. In addition, we will model longitudinally collected FOIS scores as a function of time (measured as a categorical variable) using GEEs, with additional independent variables for stratification factors and pre-RST FOIS included in all models. Comparisons at individual time points will be performed using model-based linear contrasts with inference based on associated two-sided generalized score tests. We will further evaluate the modifying and confounding effects of sex, age, smoking status, COPD status, and pulmonary function. Secondary endpoints include MDADI summary scores, and respiratory-swallow phase patterns (binary measure classified as optimal versus non-optimal) collected at all time points. Analysis of MDADI scores will follow the approach used to analyze FOIS scores. Comparisons between visits 0 and 1 respiratory-swallow phase patterns will be performed using a Rao-Scott chi-square test, an approach that accommodates comparisons of proportions from paired data with Mantel-Haenszel-type adjustments for stratification factors.¹⁰⁵ GEE models of respiratory-swallow phase patterns will be similar to those described for FOIS measures but using instead a

logit or probit link function as appropriate for binary endpoints. Results for all endpoints will be summarized separately for males and females to assess differences by patient sex.

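### The set called ITT drops randomised patients by rules that differ by arm; it is a modified ITT with unequal gates, although the expected numerical effect is small

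*Combined protocol and SAP*

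**What the plan says.** The rules are in Section 5.1, Analysis Populations.

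- **RST arm.** "Participants in the intervention arm who withdraw consent prior to completing their first training session will be replaced". Entry is then by exposure: "Those who have completed at least one RST session will contribute to the intent-to-treat (ITT) population".
- **Control arm.** "Participants in the control arm who withdraw consent prior to visit 1 will be replaced". Then: "All others in the control arm will contribute to the ITT population".
- **Use of the set.** "Efficacy will be evaluated based on the ITT population".
- **Leavers inside the set.** Those who "withdraw prior to endpoint evaluation at 6-weeks will be treated as failures (no improvement") are scored as such in the ITT analysis.

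The per-protocol set is narrower still, and no set of all randomised patients is defined. Section 5.6 states the primary comparison as "We will compare changes in MBSImp physiologic function metrics in patients randomized to intervention versus control" and uses the same phrase, "in patients randomized to intervention versus control", for FOIS. It places visit 1 after RST in the intervention arm and 4 weeks after baseline in the control arm.

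**The concern.** Control visit 1 is when the primary endpoint is measured, so the control removal window runs right up to the endpoint. The RST window closes at the first session. Take two patients who both withdraw consent in week 3: the RST patient is counted as not improved, and the control is replaced and disappears from the comparison.

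The text also leaves a gap. It does not place an RST patient who completes no session but does not withdraw consent, for example one withdrawn by the investigator under Section 5.7. Read literally, the one-session requirement leaves that patient out, while a comparable control stays in.

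MBSImP and PAS scoring is blinded to allocation, which protects the reading of the endpoint but not membership of the set. Participants and trainers know the arm. For a control, inclusion turns on whether the exit is recorded as consent withdrawal. What is at stake is a primary comparison that is labelled ITT but does not keep the randomised groups intact.

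**Working it through.** The plan gives no figure for the effect of these rules, so there is none to reproduce. The check compares the plan's set with all randomised patients, counting every leaver as not improved.

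**Inputs from the documents.** 20 per arm, two-sided alpha 0.025 and a 10% attrition allowance (Section 5.1, Power and Sample Size Justification). Section 5.6 gives 88 participants instead of 40; that is a separate conflict, and 40 is used here.

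**Assumptions.** A proportion r = 0.10 leaves each arm, unrelated to outcome. A share e of leavers goes before session 1, and a share w leaves by consent withdrawal. Central values are e = 0.25 and w = 0.5. Improvement rates are pR (RST; central 0.5) and pC (control). RST patients with no session are taken as excluded.

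**Formulas.**
- Plan: pR(1-r)/(1-re) - pC(1-r)/(1-rw)
- Common rule: (1-r)(pR-pC)

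**Central case, pR = 0.5.**

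| pC | Plan | Common rule | Shift |
|---|---|---|---|
| 0.2 | 0.45/0.975 - 0.18/0.95 = 0.4615 - 0.1895 = 0.2721 | 0.2700 | +0.002 |
| 0.1 | 0.4615 - 0.0947 = 0.3668 | 0.3600 | +0.007 |
| 0 | 0.4615 - 0 = 0.4615 | 0.4500 | +0.012 |

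**Range.** With e = 0.10 or 0.25; w = 0.25, 0.5 or 0.75; pR = 0.3, 0.5 or 0.7; and pC = 0, 0.1 or 0.2, the shift runs from -0.012 to +0.016. If half of leavers go before session 1, it reaches +0.033.

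**The gap read the other way.** If RST patients with no session who have not withdrawn consent are kept as not improved, the RST denominator is 1-rew = 0.9875 and the RST term is 0.45/0.9875 = 0.4557. The central shift becomes 0.4557 - 0.1895 - 0.2700 = -0.004 at pC = 0.2, and 0.4557 - 0.4500 = +0.006 at pC = 0.

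**Standard error.** At 0.5 v 0.2 with 20 per arm: sqrt(0.25/20 + 0.16/20) = 0.143.

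**No true effect, central mix.** With pR = pC = 0, the offset is exactly 0. At 0.1, 0.2 and 0.3 it is -0.0024, -0.0049 and -0.0073, which is against RST. The common rule gives 0 throughout.

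**Mean-change scale.** The primary test in Section 5.6 is an analysis of covariance on change, not a test of improvement rates. If controls' mean change is m, the plan's control mean is m(1-r)/(1-rw) and the common rule's is m(1-r). Both are 0 when m = 0, whatever w is. In simulated t tests at 10% leaving (20 per arm, no true effect, common mean change 0 to 0.5 SD), the rejection rate under the plan's set was 0.024 to 0.028 against a nominal 0.025.

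**Leaving related to outcome, illustration only.** Suppose the analysed set shows 12/20 v 4/20 improved: Fisher p = 0.022. If two replaced controls had in fact improved, 12/20 v 6/22 gives p = 0.060. If instead two removed patients per arm are added back as failures, 12/22 v 4/22 gives p = 0.027. The starting result was chosen to be borderline.

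**The case against.** The strongest reply is that this is a matter of labelling. Controls receive nothing for 4 weeks, and the Introduction describes the impairment as chronic and often resistant to therapy. If controls' mean change is near zero, dropping a control or scoring that control as zero gives the same expected arm mean. Dropouts are described as rare, the 10% is only an allowance, and controls have a reason to stay because RST follows at crossover. All of this stands, and it is why the expected effect is small.

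It can also be said that Section 5.6, in speaking of randomised patients, names the arms rather than the analysis set. That is a fair reading, and the point does not depend on a contradiction there: Section 5.1 alone calls the set ITT while removing randomised patients by arm-specific rules.

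A reader might infer more: that the rule biases the trial towards RST, or inflates the false-positive rate. The documents do not support that. The direction is not fixed. Leaving out RST non-starters raises the difference, while counting late RST leavers as failures and dropping control leavers lowers it. Under no true effect the offset is zero or slightly against RST in the central mix. Nor do the documents state that RST non-starters who keep their consent are excluded; that is inferred from silence, and the other reading changes the sign of the central shift at pC = 0.2.

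**Conclusion.** The defect in the wording is certain: the set named ITT is a modified ITT with unequal gates, it carries the efficacy analysis, and no all-randomised analysis stands beside it. Its expected size is small: about -1 to +2 percentage points on the improvement-rate difference against a standard error of about 14, and nothing from the control rule on the mean-change scale if controls' mean change is about zero.

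Those figures rest on 10% leaving in each arm, leaving unrelated to outcome, at most a quarter of leavers going before session 1, and the assumed improvement rates. They say nothing about leaving that differs by arm or depends on outcome. The documents give no basis for putting a figure on that; the Fisher example shows only that two patients can matter when the result is close.

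**What to change.** 1. Define the primary efficacy set as all randomised patients, analysed as assigned. Replacements may still be recruited, but the patients they replace stay in the set.
2. Apply the existing no-improvement rule to missing visit 1 data in both arms, whatever the reason for leaving, and state it as zero change for the analysis of covariance.
3. Tie the rule to visit 1, and reconcile the 6-week wording in Section 5.1 with the 4-week control visit in Section 5.6.
4. Rename the present set modified ITT, say where an RST patient with no completed session belongs, and keep the set as supportive.
5. Add a sensitivity analysis that varies leavers' assumed change separately by arm. The same penalty d in both arms would shift each mean by rd and cancel when leaving is equal, so it would not test the concern.

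The cost is SAP wording and one extra analysis. A few more patients count as not improved: about 1 to 2 controls at 5% to 10% consent withdrawal (20/0.95 = 21.1; 20/0.90 = 22.2), plus any RST non-starters. In the central case at pC = 0.2 the estimate moves from 0.272 to 0.270. The change removes the asymmetry; it does not recover leavers' true outcomes.
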